6.1 Reporting of Adverse Events

The AE reporting requirements for this study are as follows:

- All AEs that meet the definition of serious (see page 27) and occur within the perioperative period (intraoperative to hospital discharge) to 90 days following the date of surgery.
- All AEs related to the operative site, regardless of seriousness or time of occurrence.

On postoperative functional evaluations, investigators and SCs will be prompted to question subjects as to whether they have seen a doctor for any reason, been hospitalized for any reason or have a current impediment to their function.

The following decision tree facilitates identification of AEs for which reporting is required under this study protocol:

Yes

Stryker via AE eCRF

perioperative period to 90 days following date of surgery?

End

General Physical Examination Findings

At screening for inclusion into the study, any clinically significant abnormality should be recorded as a preexisting condition and reported on the Demographics eCRF. From the time of consent forward, any new clinically significant findings or abnormalities that meet the definition of a protocol defined AE must also be recorded and documented as an AE.

Adverse Event Reporting Period

The study period during which AEs must be reported is normally defined as the period from the initiation of any study procedures to the end of the study treatment follow-up. The start of study procedures is considered to be the point of consent. Any AEs which fit the protocol defined reportable events must be reported from the time of consent until study completion.

At each contact with the subject the investigator must seek information on AEs by specific questioning and, as appropriate, by examination. Information on protocol defined AEs should be recorded immediately in the source document and also in the appropriate AE module of the eCRF. All clearly related signs, symptoms and abnormal diagnostic procedure results should be recorded in the source document and grouped under one diagnosis, as appropriate. The clinical course of each event should be followed until resolution or until it is determined at the end of the study that the AE will not resolve.

All operative site events occurring at any time as well as all serious adverse events (SAEs) occurring within 90 days postoperative will be collected and compared to published data. It is expected that the AE rates reported for the Triathlon Tritanium Cone Augments will be comparable to those reported in the literature for other revision TKA systems on the market.

6.2 General Adverse Event Definitions

Following is a list of general AE definitions. For the purposes of this study, only SAEs occurring within 90 days postoperative, excluding elective procedures, as well as all AEs related to the operative site should be reported.

Adverse Event

An **AE** is any untoward medical occurrence in a clinical investigation subject, which changes the medical baseline of the subject. An AE can be an unfavorable and unintended sign, symptom or disease, whether or not related to the study device (AEs may also be referred to as complications). See Section 6.1, Reporting of Adverse Events, for the AE reporting requirements for this study.

Anticipated Adverse Event

An **anticipated AE** is an AE, of which the nature, severity or degree of incidence is known and identified in applicable product labeling, published literature or the study protocol. The list of anticipated events is provided in Section 11, Risk/Benefit Assessment.

Serious Adverse Event

A **SAE** meets one or more of the following definitions:

- Resulted in in-patient hospitalization
- Resulted in prolonged existing hospitalization
- Resulted in persistent or significant disability/incapacity
- Resulted in permanent impairment of a body function or permanent damage to a body structure
- Necessitated medical or surgical intervention to preclude permanent impairment of a body function or permanent damage to a body structure
- Was a life-threatening situation
- Resulted in patient death

Adverse Device Effect

An **adverse device effect** (ADE) is a negative change in the subject's health that may have been caused by, or associated with, the use of the device.

Unanticipated Adverse Device Effect

An **unanticipated adverse device effect** (UADE) is any serious adverse effect on health, safety or any life-threatening problem or death caused by, or associated with, a device if that effect is a problem or death not previously identified in nature, severity or degree of incidence, or any other unanticipated serious problem associated with a device and related to the rights, safety or welfare of subjects.

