6.3 Study Sponsor Notification by Investigator

Of reportable AEs, certain events must be submitted to Stryker within 24 hours for timely notification:

Adverse events that require time sensitive reporting:

An adverse event should be reported to Stryker Clinical Research either by telephone/fax/email within 24 hours of the site becoming aware of the event if any of the following apply:

- The AE occurs intraoperatively or is related to the surgical procedure.
- The AE is considered by the investigator to be device related or if the investigator is uncertain regarding the device related assessment;
- The AE required a reoperation of the study knee or a revision of any study knee components.

At the time of the initial report, the following information should be provided:

Subject number	 Whether study treatment was
A description of the event	discontinued
Date of onset	 Investigator assessment of the
Current status	association between the event and
	the study treatment

These reports will be evaluated by Stryker to determine if a Product Inquiry (PI) is required.

It is recommended that all other reportable AEs are submitted through eCRF entry within 2 weeks.

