Intraoperative fissure, fracture, or perforation of the femur or tibia can occur due to impaction of the component into the prepared femur or tibia. Postoperative femoral or tibial fracture can occur due to trauma, the presence of defects or poor bone stock.

Metal sensitivity reactions have been reported following joint replacement.

AEs may necessitate reoperation, revision, arthrodesis of the involved joint, or amputation of the limb.

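### A device-related adverse event away from the operative site has no clear reporting route to the sponsor if it is non-serious, or serious after day 90

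*Combined protocol and SAP*

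**What the plan says.** Section 6.1 of the protocol sets two reportable classes. The first is "All AEs that meet the definition of serious (see page 27) and occur within the perioperative period (intraoperative to hospital discharge) to 90 days" after surgery. The second is "All AEs related to the operative site, regardless of seriousness or time of occurrence". The end of 6.1 restates the pair: "All operative site events occurring at any time as well as all serious adverse events (SAEs) occurring within 90 days postoperative will be collected". Section 6.2 makes the pair exclusive: "only SAEs occurring within 90 days postoperative, excluding elective procedures, as well as all AEs related to the operative site should be reported". The reporting period in 6.1 runs from consent to study completion, but only for events that already qualify: "Any AEs which fit the protocol defined reportable events must be reported from the time of consent until study completion".

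Section 6.3 opens with "Of reportable AEs, certain events must be submitted to Stryker within 24 hours for timely notification". Among its criteria is "The AE is considered by the investigator to be device related or if the investigator is uncertain regarding the device related assessment". It closes by giving two weeks for all other reportable events.

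Section 6.2 also defines the adverse device effect (ADE) and the unanticipated adverse device effect (UADE). Neither definition depends on where in the body the effect appears or how long after surgery. Section 8.2.2 tabulates protocol-defined events only.

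**The concern.** A reader of 6.3 would expect the sponsor to hear within a day about any event the investigator links to the device. The opening clause of that section ties the criterion to events that 6.1 and 6.2 already collect, and neither of those has a device-related class. The criterion therefore sets how fast an event is reported, not whether it is.

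At stake is safety capture for the device under study. Some events that meet the plan's own ADE or UADE definitions would not reach the sponsor as adverse events, and they would be missing from the safety table. Sections 6.1 and 11.3 both intend a comparison of complications with published rates, and device-related events left out would make that comparison look better than it should. The wording also leaves enough room for two sites to handle the same event differently.

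**Working it through.** The plan gives no figure to reproduce here, so the check is a reading of the rules side by side.

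**Rules as written**
- Reportable = (serious and within 90 days of surgery) or (related to the operative site). Source: 6.1, 6.2.
- 24-hour notice = reportable and (intraoperative or procedure related, or device related or uncertain, or requiring reoperation or revision of the study knee). Source: 6.3.

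**Applied to a device-related or uncertain event away from the operative site**
- Serious, by day 90: reportable; the 24-hour rule applies.
- Serious, after day 90: not reportable; the 24-hour rule is not reached.
- Non-serious, by day 90: not reportable.
- Non-serious, after day 90: not reportable.

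Three of the four combinations fall outside. For instance, a serious and unanticipated device effect away from the knee on day 120 meets the UADE definition in 6.2 but neither reportable class.

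**A listed risk as an example.** Section 11.2 states: "Metal sensitivity reactions have been reported following joint replacement". It does not say where such a reaction appears. At the knee, it would be reportable at any time. Elsewhere, it would be reportable only if serious and within 90 days.

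**Search for a third route to the sponsor**
- *ADE and UADE:* both terms are defined in 6.2, but no reporting rule in the available text uses either.
- *eCRF (Appendix G):* at follow-up visits the Post-Op Events form asks whether a protocol-defined event has occurred and, if so, calls for an AE form. The device-related item and its 24-hour prompt are on that AE form, so they act only after the event has passed the same gate.
- *Free text:* the Post-Op Events form also asks about doctor visits and about anything affecting function. These answers enter the database but do not feed the table in 8.2.2. Section 6.1 has sites ask about hospitalization for any reason, whereas the eCRF item covers elective surgery only.
- *Sponsor investigation (6.5):* this depends on events submitted through the Product Inquiry System. Section 6.3 says the sponsor evaluates the reports made under it to decide whether such an inquiry is needed.
- *EC/IRB reporting (6.3.1):* this follows local requirements and is not notice to the sponsor.

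None of these is a clear adverse event route for the three combinations above.

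**The case against.** Much can be said for the plan. This is a post-market study of a cleared device, and the same narrow scope appears consistently in 6.1 and 6.2, so it looks chosen. Several other channels exist: free text on doctor visits, death as a termination reason at any time (4.3), all-cause revision and removal (8.2.2), EC/IRB reporting, and the manufacturer's own device-reporting duties noted in the clearance letter in Appendix A. These soften the consequence. They do not put the event on an AE form or in the safety table.

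A reader might infer that such events can never be reported. The documents do not support that. After its lead-in, 6.3 has a sentence that asks for notice of an adverse event if any listed criterion applies; read alone, it covers every device-related event. The phrase about relation to the operative site is undefined, and an investigator might place an implant-caused systemic reaction under it. Only fragments of the decision tree (Figure 5) are legible in the available copy, so a device-related branch cannot be excluded.

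Three further inferences should be resisted:
- *That amputation of the study limb would be missed.* It would very probably count as an operative-site event and be reportable at any time.
- *That the 90-day window should restart after cone revision.* Under 4.3, removal of all cones ends participation, so no follow-up remains for those subjects. The point would survive only for partial revisions and other reoperations.
- *That about 95% of the harm goes uncounted.* The window is 90 / (5 × 365.25) = 90 / 1826 = 4.9% of the five-year follow-up. That is a share of calendar time, not of events, and the documents give no rate for late or non-serious device-related events away from the knee.

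**Conclusion.** The concern stands as a gap on the plain reading, with real ambiguity around it. A device-related or uncertain event away from the operative site is clearly reportable only if it is serious and occurs by day 90. Otherwise it has no clear route to the sponsor as an adverse event and is absent from the safety table, even where it meets the plan's ADE or UADE definition.

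This rests on two readings: that the lead-in of 6.3 governs the sentence after it, which the exclusive wording of 6.2 and the closing line of 6.3 both support; and that an event elsewhere in the body is not treated as operative-site related. If some sites read either point more widely, the problem becomes uneven reporting across sites, which the same change would cure.

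The number of events affected is unknown and probably small. No primary, secondary or exploratory efficacy analysis changes. The point is worth acting on because the 24-hour rule shows that the sponsor wants to hear of device-related events, and the present wording works against that aim.

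**What to change.** Add a third reportable class to 6.1, including the restatement at its end, and to the limiting sentence in 6.2: *all AEs that the investigator considers device related or of uncertain relationship, regardless of body site, seriousness or time of occurrence.*

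Then align the places that depend on it:
- the lead-in of 6.3, so that the 24-hour criterion plainly covers the new class;
- the decision tree in Figure 5, if it lacks this branch;
- the Post-Op Events question on protocol-defined events, so that sites know the new class opens an AE form.

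A sentence in 6.3 saying how ADEs and UADEs are reported would put those definitions to use.

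The cost is a protocol wording change and a small number of extra AE reports. The AE form already has systemic categories and the device-related item, so it needs no new fields. Section 8.2.2 can stay as written, because the new class becomes part of the protocol-defined events it tabulates.

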6.3 Study Sponsor Notification by Investigator

Of reportable AEs, certain events must be submitted to Stryker within 24 hours for timely notification:

Adverse events that require time sensitive reporting:

An adverse event should be reported to Stryker Clinical Research either by telephone/fax/email within 24 hours of the site becoming aware of the event if any of the following apply:

- The AE occurs intraoperatively or is related to the surgical procedure.
- The AE is considered by the investigator to be device related or if the investigator is uncertain regarding the device related assessment;
- The AE required a reoperation of the study knee or a revision of any study knee components.

At the time of the initial report, the following information should be provided:

Subject number	 Whether study treatment was
A description of the event	discontinued
Date of onset	 Investigator assessment of the
Current status	association between the event and
	the study treatment

These reports will be evaluated by Stryker to determine if a Product Inquiry (PI) is required.

It is recommended that all other reportable AEs are submitted through eCRF entry within 2 weeks.

6.3.1 Ethics Committee/Institutional Review Board Notification by Investigator

Reports of AEs (including follow-up information) must be submitted to the EC or IRB according to their specific requirements. Copies of each report and documentation of EC/IRB notification and receipt will be kept with the investigator's study files.

6.3.2 Device Retrieval Process

If the study device is removed for any reason, Stryker Orthopaedics will retrieve the Triathlon TS system for analysis to help characterize potential device-related

CONFIDENTIAL

This material is the property of Stryker Orthopaedics. Do not disclose or use except as authorized in writing by Stryker.

complications. In the event that any portion of the Triathlon TS Total Knee System is removed from a study subject, the procedure outlined in the Retrieved Implant Analysis Protocol (Appendix F) should be followed, as allowed by the hospital and institution. When revision of a study subject is scheduled, the study coordinator (SC) should contact the Clinical Study Manager (CSM) or other Stryker Clinical Research personnel assigned to the project, as soon as possible.

6.4 Recording of Adverse Events

All protocol defined AEs occurring during the study period must be recorded; this includes events that occur between visit intervals. The clinical course of each event should be followed until resolution or stabilization.

6.5 Medical Monitoring

It is the responsibility of the investigator to oversee the safety of the study at his/her center. This safety monitoring will include careful assessment and appropriate reporting of AEs, as previously noted. Stryker will conduct formal investigations via the Product Surveillance Department of those AEs which are submitted through our Product Inquiry System.

7 Data Management

7.1 Database

Data will be collected at each center and entered into Stryker's Electronic Data Capture (EDC) system. The system can be accessed remotely by each investigative center and the data entered will be managed by Stryker. Subject data will be processed and monitored according to the protocol schedule by Stryker or Stryker representatives. Draft specifications to support eCRFs are provided in Appendix G and patient questionnaires are provided in Appendix H.

7.2 Confidentiality

This study will comply with the 2002 HIPAA privacy rule. As such, Stryker will only collect that information which is necessary to support the objectives of the clinical study. Stryker will take precautions to ensure that data received is as de-identified as possible. In the case that some identified information is received, Stryker will ensure that any identifying information is not reported. Study subjects will authorize Stryker to use their health information in support of the clinical study during the informed consent process. Should a subject choose to withdraw

authorization, Stryker may use data collected prior to the withdrawal of authorization in order to maintain data integrity.

7.3 Source Documents

Source data include all information, original records of clinical findings, observations or other activities in a clinical study necessary for the reconstruction and evaluation of the study. Source data are contained in source documents. Examples of these original documents and data records include: hospital records, clinical and office charts, study worksheets, laboratory notes, memoranda, subject questionnaires, pharmacy dispensing records, recorded data from automated instruments, radiographs, subject files, and records kept at the pharmacy, at the laboratories and at medico-technical departments involved in the clinical study.

All data points collected during preoperative and follow-up visits must be documented in the subject's chart. This includes range of motion values, pain and function as well as AEs and additional comments. The informed consent process should also be documented in the patient chart. Monitors, defined further in Section 9, will be comparing the eCRFs against source documents for adequacy. The monitors will seek to draw a reference between each data point on the eCRF and the subject's chart. Thus, one cannot derive pain, ROM or function based on a chart note that reads "Patient doing well." Every effort should be made to ensure complete source documentation.

Centers are required to create a source documentation plan including any applicable source documentation worksheets prior to enrollment.

7.4 Electronic Case Report Forms

The study eCRFs are the primary data collection instrument for the study. All data requested on the eCRF must be documented. All missing data must be explained. It is recommended that eCRFs be completed and electronically signed by the investigator within 2 weeks of the evaluation date.

7.5 Data Clarification Requests

If errors or omissions are noted by Stryker upon review of the data entered into the eCRFs, a query will be sent to the center within the EDC system. Queries should be answered in a clear and comprehensible manner. If the query requires a change to study data, the EDC system will update the eCRF automatically with the data captured in the query response. The investigative center will be required to reapply their electronic signature to the modified eCRF. Modified eCRFs need not be printed and included in conjunction to answered queries.

CONFIDENTIAL This material is the property of Stryker Orthopaedics. Do not disclose or use except as authorized in writing by Stryker.

7.6 Protocol Deviations

Any major deviation from this protocol will be recorded in Stryker's Clinical Trial Management System and must be reported to the EC/IRB by the investigational site according to their reporting procedures. Major protocol deviations for this study may include the following; this list may not be all-inclusive:

- Informed consent deviations, including but not limited to:
 - Study procedures performed prior to informed consent
 - o Incorrect informed consent version used
- Patient enrolled does not meet the inclusion/exclusion criteria
- Protocol specified study component(s) not implanted
- Visit deviations, including:
 - o Unavailable primary endpoint

If the center anticipates a possible protocol deviation, the investigator or SC should contact Stryker for guidance.

7.7 Records Retention

It is the investigator's responsibility to retain study essential documents for 2 years after the date of the final report, or 2 years after the date of investigative center termination. These documents should be retained for a longer period if required by an agreement with Stryker.

8 Statistical Plan

8.1 Study Objectives

8.1.1 Primary Objective Analysis

The primary efficacy parameter is the revision/removal of femoral cone augment or tibial cone augment for aseptic loosening at 2 years postoperative.

8.1.2 Secondary Objective Analyses

The secondary efficacy parameters include:

- The end-of-stem pain shin pain and thigh pain at 2 years
- The intraoperative AORI classification, size, and shape of the femoral or tibial cone augment

CONFIDENTIAL

This material is the property of Stryker Orthopaedics. Do not disclose or use except as authorized in writing by Stryker.

8.1.3 Exploratory Objective Analysis

The exploratory efficacy parameter is the KSS objective knee score at 2 years postoperative for cases which received the Triathlon TS Total Knee System with a Triathlon Tritanium Central Femoral Cone Augment.

8.1.4 Primary Efficacy Hypothesis

The primary hypothesis to be tested will be that the success rate at 2 years postoperative with the Triathlon Tritanium Cone Augments is not worse than 97.2% with a non-inferiority margin of 2.5%. That is, the following hypothesis will be tested:

Ho: Pt <= 97.2% - 2.5% HA: Pt > 97.2% - 2.5%

Here, Pt is the success rate at 2 years postoperative with the Triathlon Tritanium Cone Augments. A case success at 2 years is defined as no incidence of revision/removal of femoral or tibial cone augment for aseptic loosening within 2 years.

